- **Function.** Standardized grip strength, standing balance, chair stand test, timed up-and-go (TUG), timed stair ascent and timed stair descent, 4 meter walk test and the 6 minute walk will be assessed. Grip strength will determine changes in each hand grip over time. Standing balance will measure changes over time in balance. The chair stand test measures the time it takes for

the subject to stand and sit five times. TUG will measure the time (seconds) needed to stand from a chair, walk 3 meters, turn around, walk back and be seated again. Timed stair ascent (10 steps) and descent will be recorded. The 4 meter walk will tell us how long it takes you to walk a short distance (4 meters) while the 6 minute walk will measure the distance you can walk over a longer distance (total distance in 6 minutes). We have experience with these functional measures. Each functional mobility measure will be performed on a single standardized chair (TUG) and stairs. Functional assessments will not be performed in a fasting state. Functional measurements may be performed at either the [name] Lab on the University of Oregon campus or the Slocum Center for Orthopedics & Sports Medicine.

- **Strength & central activation deficit.** Co-Investigator [name], PhD, will contribute her expertise to quantify pre- and post-operative changes in strength and quadriceps activation (24). Strength will be quantified using a Biomed +/- tests for central activation deficits (CAD). CAD contributes to early weakness following TKA, and [name] will quantify this progression between groups over time using previously published methods will be followed (23, 44, 62, 65, 67, 112). Voluntary activation of the knee extensor muscles will be assessed through the painless method of supramaximal magnetic stimulation of the femoral nerve superimposed on the MVC (90). Central activation of the knee extensors will be calculated from the resulting force as follows: $(MVC/(MVC + Stimulation)) \times 100$ (65). Nerve function will be determined using the latency of the M-wave in response to supramaximal magnetic stimulation of the femoral nerve (23, 44). Additionally, pre-post surgery measures of the area of the negative peak of the M-wave will be used to estimate motor neuron loss (67). Strength and central activation deficits will not be performed in a fasting state. Central activation is measured on the University of Oregon campus or at the Slocum Center.

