- **Patient-reported outcome measures.** Patients will be asked to complete questionnaires assessing self-reported quality of life, knee-specific functioning and pain.
 1. **VR-12** - Consists of select items from the eight concepts of health in the SF-12, summarized in a physical component summary and a mental component summary. Useful in understanding health-related quality of life, and differences in disease burden. Administered at Slocum per standard of care via iPads.
 2. **KOOS** - Well-established standardized knee-specific functional outcomes tool. Used frequently in the literature to report degree of functional mobility and knee-related disability. WOMAC scores may be calculated from KOOS. Reviewers may expect KOOS/WOMAC data collection use in orthopedic clinical trials. Administered on paper for research purposes.
 3. **Oxford Knee** - Shorter knee-specific functional outcomes tool. Suggested to have superior validity, reliability and responsiveness compared to older knee-specific outcome tools. Well established for use in Europe, and has gained significant traction in the United States over the past few years. Reviewers may expect Oxford data collection use in orthopedic clinical trials. Administered at Slocum per standard of care via iPads.
 4. **Visual Analogue Pain Scale (VAS)** - Measures self-reported pain, which is associated with functional outcomes in orthopedic clinical trials. Administered at Slocum per standard of care via iPads.

Covariate Measures.

There are a number of study-related activities employed to allow the study statisticians to isolate the effect of EAA supplementation on primary and secondary outcome measures (described above).

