**Inpatient Research Protocol & Integration w/ Standard Patient Care: Protocol while subject is inpatient (IP) on orthopedic floor (estimate 2 to 3 days as IP); Daily AM fasting blood draw by phlebotomist on POD 0 and POD 2. (leave blood on ice, research staff to pick up); Subject to don accelerometer at all times; Twice daily ingestion of supplement (subject and investigators are blinded to treatment group); Ingestion will occur 1 hour after daily physical therapy; Inpatient physical therapy to begin at 9 AM and 1 PM. Therapy per MD/PT standard Tx; Twice daily ingestion of deuterium oxide (D₂O); Daily food-log recordings (all nutrient intake) by subject. Research staff and nursing to remind subject to complete this task.

Specific Aim #2 (Physiology).

Aim #2 - Determine if short-term prevention of atrophy, weakness, and functional mobility leads to positive changes in muscle cell structure and function, and quality of life in the long term (6 months post-TKA) vs. Placebo.

Randomization Assignments.

- Aim #2, Trial #1 enrolled 19 patients before closing enrollment in June 2018. Please refer to the Event Form submitted on June 4, 2018 for additional details. Please refer to study protocol December 2017 for information on Aim #2, Trial #1 EAA proportions and protocols.
- Aim #2, Trial #2 (reflected throughout the protocol as "Aim 2") will consist of 2 groups (N=40/group through protocol completion; EAA vs. Placebo) that are identical in protocol design. Up to 160 patients will be consented to achieve 40 per group completion.

Summary of Study-Related Activities.

- Patient questionnaires before and after surgery
- Functional mobility tests before and after surgery
- Accelerometer before surgery and after surgery
- Optional muscle biopsy before and after surgery

Changes to Study-Related Activities.

Omitted Procedures or Measures for Participants Enrolled in Aim #2

- No strength & central activation testing
- No consumption of heavy water (D₂O)
- No muscle biopsies at surgery, 1 week or 2 weeks post-TKA operation
- No blood draws
- No MRIs performed
- No Three day food diary
- Removal of 6 minute walk
- Removal of study questionnaires at 2 weeks post-TKA (functional testing remains)

New or Altered Study Procedures or Measures for Participants Enrolled in Aim #2.

- New study assessment time points: 3 months & 6 months
- Optional (patient choice at enrollment) muscle biopsies at pre-op, 6 weeks & 6 months post-TKA

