- Option for patients with surgery dates less than 4 weeks prior to surgery to be enrolled in the functional testing arm only
- Option for patients who are taking Coumadin/Warfarin to be enrolled in the non-biopsy arm of the study
- Biopsies will be closed with suture and/or steri-strips
- Addition of the pain and catastrophizing questionnaire (covariate measure)

The procedure schedule can be referenced in Figure 2 (page 23, following a description of all study-related procedures and measures for Aim #2).

[figure not shown]
Primary Physiological Outcome Measures. Consistent with the Secondary Outcome Measures described in Aim #1 (please refer to Aim #1) aside from the omitted and new/ altered procedures noted above (see Changes to Study-Related Activities in this section), but followed over a longer period time (6 months).

Secondary Physiological Outcome Measures. Consistent with the *Primary Outcome Measures* described in Aim #1 (please refer to Aim #1) aside from the omitted and new/ altered procedures noted above (see Changes to Study-Related Activities in this section).

Covariate Measures. Consistent with the *Covariate Measures* described in Aim #1 (please refer to Aim #1 above), with the addition of the pain and catastrophizing scale (questionnaire)

Aim #2 Study Activities Timeline. Participants will be enrolled for up to six months prior to surgery through 6 months post-operatively. Figure 2 (next page) describes the schedule of study-related events, including evaluable time windows, under Study Aim #2.

Overview of Aim #2 study timeline, activities, measures and procedures.

Schedule of Events									
Time	-6 mo max	-8 wks to -1 wks (+ 1 day)	-1 wk (± 0 day)	TKA (Day 0)	2 wk (± 1 week)	6 wk (± 1 week)	3 mo (± 2 weeks)	6 mo (± 2 weeks)	
Enrollment	X	X							
Screening	X	X							
Questionnaires		X				X	X	X	
Functional Mobility Test		X			X	X	X	X	
Accelerometer		X ^A				X	X ^A	X ^A	
Supplement [*]			start → Stop						
Bilateral Muscle Biopsy ^B		X ^B			X			X	

Functional testing & biopsy: Performed at the [name] Lab, University of Oregon or the Slocum Center.

^A Subjects will have the accelerometer ON daily during waking hours (off while sleeping and showers) for a 7 consecutive day period ending at this time point.

^B Optional muscle biopsy as per patient choice; Biopsies must be completed a minimum of 4 weeks prior to TKA; patients who are enrolled between

-4 weeks and -1 week (+ 1 day) will not be eligible to participate in the biopsy arm.

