Power analyses. For our power calculations, we have assumed a Type I error rate (α) of $.05$, two-tailed. We based power calculations on effect sizes (d) that we derived from analysis of preliminary data preliminary data and prior studies (10, 30, 32, 33, 36, 41, 51, 113). We calculated d as the standardized mean difference between treatment conditions at follow-up: $d = (x_C - x_T)/S$, where x_C represents the primary outcome mean in the Placebo and EAA conditions and S is the pooled standard deviation, after adjusting x for pretest scores and covariates (sex, tourniquet time, age, body mass index, fat/carbohydrate/protein intake).

We propose to enroll **40 total subjects for Aim 1** who are retained through protocol completion (20/group, EAA and Placebo, randomized to either 1 week or 2 week post-operative biopsies), and **80 total subjects** (40/group, EAA and Placebo) **for Aim 2** who are retained through protocol completion to account for possible attrition and to ensure sufficient power to test the hypotheses that EAA therapy up-regulates basal levels of muscle protein synthesis, and reduces post-operative atrophy bilaterally, preserves quadriceps strength, and improves functional mobility relative to a Placebo condition.

Effect sizes. Effect sizes were as follows: (a) Cell and FSR data: REDD1 $d = 1.24$, SLC36A2 $d = 1.27$, and FSR $d = 1.51$ (FSR calculated from mean change from baseline). The mean effect across outcomes was $d = 1.37$, reflecting large effects. (b) Physiological and functional data (percent change from Baseline to 6 wk): operative quadriceps volume $d = 1.52$, and isometric strength $d = .90$; non-operative quadriceps volume $d = 1.05$, and isometric strength $d = .66$; timed up-and-go test $d = 1.03$, timed stair ascent $d = 1.08$, timed stair descent $d = 1.13$, and six-minute walk test $d = .70$. Mean effect size was $d = 1.01$, reflecting large effects.

Power calculations. Power calculations were based on the sample size and minimally detectable ES (MDES) as follows:

- **Aim #1:** For a sample size of 20 completed subjects/group (10/group for metabolic studies, however, EAA vs. Placebo = 20 total EAA and 20 total Placebo). Aim 1, proposed study can detect

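### Aim 2 labels 7 to 11 outcomes primary without naming a primary outcome, a primary visit or a multiplicity rule, so a 5% error rate for its conclusion is not secured

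*Combined protocol and SAP*

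**What the plan says.** Under Specific Aim #2, Primary Physiological Outcome Measures, the primary outcomes are "Consistent with the Secondary Outcome Measures described in Aim #1", apart from omitted and altered procedures, followed over six months. The Aim 1 secondary list contains muscle volume, edema, function, strength and activation, and patient-reported outcomes.

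The Aim 2 list of omitted procedures includes "No MRIs performed", "No strength & central activation testing" and "Removal of 6 minute walk". Two groups clearly remain:

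- Function: "Standardized grip strength, standing balance, chair stand test, timed up-and-go (TUG), timed stair ascent and timed stair descent, 4 meter walk test", which is seven tests.
- Patient-reported outcomes: "Patients will be asked to complete questionnaires assessing self-reported quality of life, knee-specific functioning and pain", using VR-12, KOOS, Oxford Knee and the pain scale, which is four instruments.

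The Aim 2 schedule places functional tests at 2 weeks, 6 weeks, 3 months and 6 months, and questionnaires at the last three of these. Appendix 1 describes each functional test as a study endpoint. It describes the four questionnaires as material for analysis, stratification or covariate use.

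In Data Analysis the only alpha appears under Power analyses: "we have assumed a Type I error rate" of .05, two-tailed, for the power calculations. ANCOVA is to answer the research questions of both aims. Random coefficients models are to describe trajectories, with condition tested through its interaction with time.

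**The concern.** When several outcomes share the primary label and no rule says which one decides, or how many must succeed, a significant result on any of them can be presented as the primary finding. Nothing in the plan then holds the overall error rate at the 5% assumed for a single test.

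The decisive time is also open. Question 2.1 is short-term (given as 7 weeks post-TKA, although the schedule has a 6-week visit). Questions 2.3 and 2.4 concern 6 months. What is at stake is how much weight an isolated positive result from Aim 2 could bear.

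**Working it through.** **The plan's own figure.** The documents state no familywise error rate. The nearest figure is the Aim 2 detectable effect: d > .79 with 40 per group and 85% power. A two-sample t calculation at two-sided .05 gives d = 0.68; the normal approximation is (1.960 + 1.036) × √(2/40) = 0.67. The stated .79 fits about 29 to 30 per group. The plan's covariate steps do follow from .79: .79 × √(1 − .50²) = .684 and .79 × √(1 − .75²) = .523. This mismatch is a separate matter, errs on the cautious side and does not enter the error rates below.

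**Number of outcomes.** Seven functional tests, plus four questionnaires if they count as endpoints: 7 or 7 + 4 = 11. All 11 are measured at 6 weeks, 3 months and 6 months; only the 7 functional tests are measured at 2 weeks. Separate VR-12 physical and mental scores would make 12. Edema is left out because it needs an optional biopsy and Appendix 1 treats it as confounder control.

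**Error rate at one visit, all null hypotheses true.** For m independent tests:

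- Either direction: 1 − .95^m. For m = 7, 1 − .95^7 = 30.2%. For m = 11, 1 − .95^11 = 43.1%.
- Favouring EAA only, at 2.5% per test: 1 − .975^m. For m = 7, 16.2%. For m = 11, 24.3%.

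For correlated tests, the statistics were taken as standard normal with a common pairwise correlation ρ, and the chance that none crosses 1.96 was integrated numerically.

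| Assumed ρ | 7 tests, either direction | 7 tests, favouring EAA | 11 tests, either direction | 11 tests, favouring EAA |
|---|---|---|---|---|
| 0 | 30.2% | 16.2% | 43.1% | 24.3% |
| .3 | 27.1% | 13.7% | 37.5% | 19.1% |
| .5 | 23.0% | 11.5% | 30.4% | 15.2% |
| .7 | 17.8% | 8.9% | 22.3% | 11.1% |

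**Power cost of adjustment, 40 per group, noncentral t, no covariate.** Bonferroni over 7 uses .05/7 = .0071 per test. Holm is never less powerful than Bonferroni over the same tests.

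| True d | Unadjusted .05 | Bonferroni over 7 |
|---|---|---|
| 1.13 (pilot, stair descent) | 99.9% | 98.8% |
| 1.03 (pilot, timed up-and-go) | 99.5% | 96.5% |
| .7 (assumed) | 87% | 64% |
| .5 (assumed) | 60% | 31% |

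Among the retained outcomes, the documents give pilot effects only for timed up-and-go, stair ascent and stair descent, and only from baseline to 6 weeks.

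**The case against.** The strongest reply is that the plan never says every outcome will be tested separately at .05. The alpha belongs to the power section, and the random coefficients model would give one condition-by-time test per outcome rather than one per visit. This stands: the supportable criticism is that the decision rule is missing, and the rates above are conditional on per-outcome testing at .05. It does not remove the problem. One test per outcome is still 7 to 11 tests, and the plan does not say whether ANCOVA or the random coefficients model decides.

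A second reply is that the questionnaires are not endpoints, since Appendix 1 describes them differently from the functional tests. The Aim 1 secondary list does include them, so the documents are ambiguous and both counts are reported.

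Two stronger readings are tempting but not supported:

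- A reader might take 22-43% as the chance of falsely concluding that EAA works. Those figures include false differences favouring placebo. The matching range favouring EAA is 11-24% for 11 tests.
- A reader might count 7 × 4 + 4 × 3 = 40 outcome-by-visit tests and quote 1 − .95^40 = 87%. That treats repeated visits on the same patients as independent. It also goes beyond questions 2.1 and 2.3-2.4, none of which asks for a separate test at 2 weeks or 3 months, and it ignores the planned time-by-condition model.

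Finally, adjustment cannot be called cheap for every outcome. The high retained power rests on three tests with 6-week pilot effects.

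**Conclusion.** The concern holds in this form: Aim 2 has 7 to 11 outcomes under the primary label and no rule for which outcome, visit or model decides. Under testing at two-sided .05 at one visit, the chance of at least one false significant difference is 18-30% (7 tests) or 22-43% (11 tests) in either direction. Favouring EAA it is 9-16% or 11-24%, against 2.5% for a single two-sided test.

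The ranges rest on three assumptions: an equal correlation of .7 down to 0 between outcomes, no true effect on any outcome, and per-outcome testing at .05, which is inferred from the power section and the absence of any adjustment. This should be corrected; it needs a change of wording, not of design.

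**What to change.** Before unblinded analysis, amend the Aim 2 outcome and Data Analysis sections as follows.

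1. Name one primary outcome and one primary visit. Choose the visit to match the question the aim is meant to answer: short-term (2.1) or 6 months (2.3-2.4). A functional test with pilot support, such as timed stair descent (d = 1.13 at 6 weeks, pre-post r = .78), is one candidate. Its pilot effect does not cover 6 months, and an early primary visit would move the aim's long-term question to secondary status, so the choice should be deliberate.
2. State whether ANCOVA or the random coefficients model gives the deciding test.
3. Test the primary at two-sided .05 and apply Holm to the other functional tests at that visit. If 5% is to cover both steps together, proceed to Holm only when the primary is significant.
4. Label the questionnaires and other visits secondary, and align Appendix 1 with the outcome section.

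No visit, assessment or participant is added, and the named primary loses no power to adjustment. The non-primary functional tests do lose power: Bonferroni over 7, a lower bound for Holm here, keeps about 97-99% at the pilot effects, but 64% at an assumed d of .7 and 31% at .5.
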